- 1) Propranolol 160 mg PO will reduce the resting EE measured at a temperature just above the subject's placebo shivering threshold (REE_{Low}) by greater than or equal to 5% compared to placebo REE_{Low} . If propranolol-treated subjects shiver at the low temperature, then measurement of non-shivering EE is not possible in this protocol. Propranolol will be judged to increase the shivering threshold if significantly more subjects shiver with propranolol than with placebo treatment.
- 2) Pindolol 20 mg PO will lead to a similar difference in resting EE measured at thermoneutrality ($REE_{27^\circ C}$) and REE_{Low} .
- 3) Dantrolene 100 mg PO will reduce the REE_{Low} by greater than or equal to 5% compared to placebo REE_{Low} . If dantrolene-treated subjects shiver at the low temperature, then measurement of non-shivering EE is not possible in this protocol. Dantrolene will be judged to increase the shivering threshold if significantly more subjects shiver with dantrolene than with placebo treatment.
- 4) Magnesium sulfate (50 mg/kg bolus followed maintenance infusion at 2 g/h) will reduce the REE_{Low} by greater than or equal to 5% compared to REE_{Low} .

Cohort 2

- 1) To evaluate the effect of caffeine (300 mg PO) on BMR ($=REE_{27^\circ C}$).
- 2) To evaluate the effect of Qsymia (topiramate 92 mg CR, phentermine 15 mg PO) on BMR.

- 3) To evaluate the effect of phentermine (37.5 mg PO) on BMR.
- 4) To evaluate the effect of topiramate (200 mg PO) on BMR.
- 5) To evaluate the effect of naltrexone (100 mg PO) on BMR.

Hypotheses

- 1) Caffeine 300 mg PO will increase BMR by greater than or equal to 5% vs placebo.
- 2) Qsymia (topiramate 92 mg CR, phentermine 15 mg) PO will increase BMR by greater than or equal to 5% vs placebo.
- 3) Phentermine 37.5 mg PO will increase BMR by greater than or equal to 5% vs placebo.
- 4) Topiramate 200 mg PO will increase BMR by greater than or equal to 5% vs placebo.
- 5) Naltrexone 100 mg PO will increase BMR by greater than or equal to 5% vs placebo.

Cohort 3 – This Cohort has completed enrollment

- 1) To compare the effects of mirabegron at 0mg, 50mg, and 200mg on BAT metabolic activity.
- 2) To compare the effects of mirabegron at 0mg, 50mg, and 200mg on BMR.

Hypotheses

- 1) Mirabegron at 50mg and 200mg PO will each increase BMR and BAT activity more than placebo.
- 2) The increases in heart rate and systolic BP after a one-time dose of 50mg will be lower than that observed using 200mg.

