II.2 Secondary Objectives

For all available conditions (temperature and drug/dosage), the following will be reported (when not already reported as a primary objective):

- 1) resting EE using metabolic chamber (Cohorts 1, 2 and 3)
- 2) difference in resting EE (Δ EE) between REE_{27°C} and REE_{Low} (Cohort 1),
- 3) comparison between placebo Δ EE (Cohort 1) and Δ EE for each drug (Cohorts 1, 2 and 3)

4) difference between drug and placebo resting EE (at the same temperature) (Cohorts-1, 2 and 3)

II.3 *Exploratory outcomes*

1) resting respiratory quotient (RQ): although it is a short-term measure that reflects net macronutrient utilization. Our current data in the protocol 12-DK-0097 suggest that this is also correlated with ambient temperature.

2) difference in resting RQ between $RQ_{27^\circ C}$ and a temperature just above the subject's placebo shivering threshold RQ_{Low} ,

3) difference between drug and placebo resting RQ (at the same temperature)

4) skin and core body temperature

5) heart rate and its variability

6) shivering by surface electromyography and accelerometry

7) hormonal changes that occur with NST by characterizing the effect of placebo and drug regimens on the following analytes, measured fasting at the end of each chamber session.

Urine:

norepinephrine
epinephrine
free cortisol
creatinine
volume

Plasma:

norepinephrine	Adiponectin
epinephrine	Ghrelin
glucose	Gastric inhibitory polypeptide (GIP)
insulin	Peptide YY (PYY)
free fatty acids	Glucagon-like peptide-1 (GLP-1)
β -hydroxybutyrate	Leptin
T3	Growth hormone
T4	fibroblast growth factor 21 (FGF21)
TSH	irisin ⁹²
Glucagon	atrial natriuretic peptide (ANP) ⁹³
Cortisol	ventricular natriuretic peptide (BNP) ⁹³
Parathyroid Hormone (PTH)	Adrenocorticotrophic hormone (ACTH)

III. Study Protocol

III.1 Subjects and Recruitment

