Power calculation: To estimate power, we used data from 12-DK-0097. We first determined that the within-subject difference in the response in BMR within TNZ was normally distributed with a standard deviation of 2.54%. The maximum NST in 9 young healthy male subjects was $17.4 \pm 3.7\%$. With 12 subjects completing the protocol, if the true difference in the mean response to treatment is 5.0% as we hypothesized for each drug treatment, we will be able to reject the null hypothesis that this response difference is zero with probability (power) of 0.98 at an alpha of 0.05 in either Cohort. Since this study is designed to use the pharmacological agents only to test the mechanisms of NST and BMR, thus we will not compare any pharmacological interventions to each other. However, in the most conservative interpretation, multiple comparisons adjustments will only be necessary for the number of paired comparisons between drugs and placebo within each Cohort. The result of such a conservative estimate of power range from 0.92 at an alpha value of 0.01 (0.05/5, the Bonferroni method) in Cohort 2 to 0.94 in Cohort 1 (alpha = 0.05/4). Even if the true difference was 3%, the power to detect with n=12 is above 0.83 in all analyses. To consider in potential dropouts (about 30%), we will recruit 16 subjects for each cohort (subjects can participate in both with a minimum of 2 weeks washout in between the studies), aiming to have 12 completers for each cohort.

In Cohort 3, the primary endpoint is the difference in detectable BAT activity (units of $\text{mL}^* \text{SUVmean}^* \text{g/mL}$) between the 0 mg and 50 mg doses of mirabegron. Based on our previous study ([name] et al., 2015), BAT activity is right-skewed and not

normally distributed, so our sample size determination is based on log BAT activity, which is normally distributed. We found that log BAT activity after treatment with 0 mg mirabegron was 0.05 ± 0.62 and after treatment with 200 mg mirabegron was 2.00 ± 0.79 . Since it is unknown what the effect of 50 mg mirabegron would be on BAT activity, we calculated a range based on lower and upper bound expectations about the reported PK/PD profile of mirabegron. For the lower bound, the 50 mg dose has been found to have a mean plasma C_{max} that is 18% of 200 mg. If there were a linear relationship between BAT activity and dose, then we would predict 50 mg to produce a mean log BAT activity of 0.36.

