The first study visit will involve a 6-hour stay in the metabolic chamber. Each study volunteer will also be fitted with a cooling vest (CFA-9 vest, Polar Products, Stow, OH) while in the chamber. The first 240 minutes (4 hours) will be an acclimatization period with BMR measurement; the temperatures of the chamber and the water vest will be set at 20°C. At +240 minutes, the study team will reduce the temperature of the water

in the cooling vest to 14.0-16.0°C by turning on the vest pump which will be set up on the outside of the metabolic chamber. The tubing that circulates the chilled water through the vest will be placed through the access port of the chamber so that there is no disruption to the metabolic chamber data collection. Subjects may continue usual sedentary activities during this time. After 60 minutes of cooling, the volunteer will be injected with ¹⁸FDG for PET scan. Those subjects with detectable BAT (by PET/CT) will then proceed to the additional study days in which they will receive oral mirabegron at 0mg, 50mg, and 200mg. If there is not sufficient detectable BAT after cold exposure, subjects will only complete the study day with mirabegron at 200 mg, not 0 mg or 50 mg. This will serve as a control for the differences in the amount of increase EE due to drug versus cold independent of BAT presence.

The second, third and fourth study visits will be conducted similarly. Volunteers will enter the metabolic chamber at 8:00 am for daily BMR measurements while exposed to a room temperature of 27.0°C. After a 60 minute acclimatization period, the drug or placebo will be administered in a randomized fashion at time -0- (9:00 am ± 15 minutes). Blood samples will be obtained at -0-, +15, +30, +60, +120, +180, +240, +315, +360, and +420 minutes. At +240 minutes of mirabegron administration, the volunteer will be injected with ¹⁸FDG for PET scan.

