For each study day (A, B, C, and D), a dose of [¹⁸F]-fluorodeoxyglucose (FDG) will be given at 13:00 (+60 minutes of cold exposure or +240 minutes of mirabegron administration) and the volunteers will remain in the chamber for an additional 60 minutes to allow for uptake of the radiotracer. Volunteers will then exit the chamber and be transported via wheelchair to the Clinical Center Nuclear Medicine Department for a positron emission tomography/computerized tomography (PET/CT) scan at 14:30. The scan will take no more than 60 minutes. Immediately upon completion of the PET/CT, subjects may be transported to the Radiology Department for a Magnetic Resonance Imaging (MRI) study. This scan will take no more than 60 minutes, as well. Following completion of the PET/CT and MR imaging, volunteers will then return to their room on the Metabolic Clinical Research Unit where they may have a meal and then may be discharged. Volunteers will be instructed to return for the next study visit until testing is complete.

For each chamber study, volunteers will be fasted after midnight and during the 8-hour study period they are in the chamber followed by PET/CT and MRI. During this time, all volunteers will be asked to minimize their physical activity while staying awake in a reclining position in the designated chair in the chamber. Between 08:30-09:00 10:30-11:00, and 12:40-13:10, the volunteer is required to lower the ambient lighting and recline without any physical activity, but remain awake. Clothing will be standardized and limited to the following: one pair of undershorts, one short-sleeve hospital scrub shirt, one pair of hospital scrub pants, and one pair of light socks (provided by the inpatient unit), for a combined thermal insulation value of 0.4 (clo).⁹⁴

III.3 Inclusion Criteria:

- Generally healthy
- Males between the age 18-35 years
- Written informed consent.

III.4 Exclusion Criteria:

- BMI less than 18.5 or greater than 25.0 kg/m²
- History of cardiovascular disease such as congestive heart failure, heart block, clinically abnormal EKG as determined by investigators.
- History of a cerebrovascular accident (CVA) or seizures.
- History of liver disease or ALT serum level greater than two times the laboratory upper limit of normal
- History of kidney diseases or renal insufficiency or estimated creatinine clearance ≤ 50 mL/min (MDRD equation)
- History of cancer or bariatric surgery
- History of diabetes mellitus or fasting serum glucose > 126 mg/dL

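### Cohort 3 schedules a standardised pre-dose rest window on every dosing day, but the plan gives that reading no role in the BMR comparison of 0, 50 and 200 mg

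*Combined protocol and SAP*

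**What the plan says.** Section II.1 lists two Cohort 3 objectives. The second is "To compare the effects of mirabegron at 0mg, 50mg, and 200mg on BMR", and the matching hypothesis is "Mirabegron at 50mg and 200mg PO will each increase BMR and BAT activity more than placebo". Neither says whether an increase is measured from a pre-dose value.

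Section II.2 gives the only EE contrast that fits the Cohort 3 dosing days: "difference between drug and placebo resting EE (at the same temperature". It has no pre-dose term. The other comparison in II.2 that names Cohort 3 uses the difference between 27°C and the low temperature, and the Cohort 3 dosing days are all at 27°C.

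Section III.2-3 sets out those days. Chamber entry is at 08:00, with the room held at 27°C. Dosing comes an hour later: "After a 60 minute acclimatization period, the drug or placebo will be administered in a randomized fashion". The nominal time is 09:00, with a tolerance of 15 minutes either way. For the rest periods: "Between 08:30-09:00 10:30-11:00, and 12:40-13:10, the volunteer is required to lower the ambient lighting and recline without any physical activity". At the nominal dosing time, the first window is pre-dose and the other two are post-dose. Clothing, fasting and posture are the same in all three.

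The power section in III.1 sizes Cohort 3 on another outcome: "the primary endpoint is the difference in detectable BAT activity" between 0 and 50 mg. No sample size or power is given for BMR.

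**The concern.** In a crossover each man is his own control, so stable differences between men already cancel. What remains in a drug-minus-placebo contrast is variation between days within a man. A resting EE reading taken on the same day before dosing may share part of that variation, and adjusting for it would then narrow the interval for the drug effect without collecting anything new.

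The 50 mg comparison has consequences. The mirabegron part of section I.2 says the 50 mg dose goes forward if it is effective enough, and that a combination will otherwise be considered. The cohort could also end at the interim analysis with 12 completers, where precision is weakest. With no model named, the analyst can choose afterwards between the raw post-dose difference, a change from pre-dose and a covariate adjustment. These three can differ materially in precision.

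**Working it through.** **The plan's own figure.** The stated N of 28 is for log BAT activity: difference 0.36, SD 0.66, alpha 0.05 (taken as two-sided), power 80%. Normal approximation: (1.960 + 0.842)² × (0.66/0.36)² = 7.85 × 3.36 = 26.4, so 27. The exact noncentral t gives 29, with power 79.5% at 28. For a difference of 1.00 the exact t gives 6, as stated. Both figures are reproduced within tolerance. BMR does not enter them.

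**Inputs for BMR, all assumptions for this cohort.**
- Effect of 50 mg: 18% (the Cmax ratio in III.1) × 13% (the pilot rise in resting metabolic rate, I.2) = 2.34%. This applies the plan's lower-bound reasoning for BAT to EE by analogy.
- SD of the paired difference: 2.54%, borrowed from the Cohort 1 and 2 power calculation. If that figure is a per-measurement SD, the SD of a difference is 2.54 × √2 = 3.59%.
- ρ, the within-subject correlation between pre-dose and post-dose EE across days: not in the documents, so ranged.

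**Unadjusted power, paired t, effect 2.34%.**

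| n | SD 2.54% | SD 3.59% |
|---|---|---|
| 12 | 0.827 | 0.540 |
| 28 | 0.997 | 0.914 |

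**Adjusted precision, joint three-dose model** (dose, period, fixed subject effects). Residual df without the covariate: ν = 3n − n − 2 − 2 = 2n − 4. Estimating the slope costs one df and inflates the variance by about 1 + 1/(ν − 2). The CI width ratio is therefore about

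√(1 − ρ²) × √(1 + 1/(ν − 2)) × t(ν − 1)/t(ν).

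- n = 12: ν = 20; √(1 + 1/18) × 2.0930/2.0860 = 1.031.
- n = 28: ν = 52; √(1 + 1/50) × 2.0076/2.0066 = 1.010.

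| ρ | n = 12 | n = 28 |
|---|---|---|
| 0 | 1.03 | 1.01 |
| 0.2 | 1.01 | 0.99 |
| 0.3 | 0.98 | 0.96 |
| 0.5 | 0.89 | 0.87-0.88 |
| 0.7 | 0.73-0.74 | 0.72 |

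Simulation of the same model with balanced sequences agrees to within about 0.01. Break-even is near ρ = 0.24 at n = 12 and 0.14 at n = 28.

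**Pairwise version.** Regressing the 50-minus-0 mg post-dose difference on the pre-dose difference uses less information. The ratio is √(1 − ρ²) × √((n − 2)/(n − 3)) × t(n − 2)/t(n − 1). At ρ = 0 it is 1.07 (n = 12) and 1.02 (n = 28), with break-even at about 0.35 and 0.2. For n = 12 and SD 3.59%, power moves from 0.54 to 0.49 (ρ = 0), 0.61 (0.5) or 0.77 (0.7).

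**Simple change score.** The ratio is √(2(1 − ρ)): 1.41 at ρ = 0, 1.18 at 0.3, 1.00 at 0.5 and 0.77 at 0.7. It helps only above 0.5.

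**The case against.** A reader might infer that the protocol has decided to compare post-dose values only. The documents do not say so. The objective names no estimator, the hypothesis can be read as change against change, and a rest window placed just before dosing (Cohort 1 has none) is consistent with an intended baseline. The plan is silent on the reading; it does not exclude it. That stands.

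A reader might also infer that adjustment must sharpen the 50 mg result at no cost. That depends on ρ, and a high value cannot be presumed. The window falls inside the acclimatisation hour, the metabolic chamber section in III.5 requires minimal activity only after the first 30 minutes, and the last post-dose window is about four hours later. Sleep and the evening meal are already controlled (III.5), which leaves less day-to-day noise to remove. This stands as a limit on the gain. It is not a reason to leave the model open, because the worst case in the joint model is about 3%.

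Power gains at 12 completers with a 2.34% effect join two scenarios the plan keeps apart, since it expects to stop at 12 if the response is nearer its upper bound. By the same analogy the upper bound is at least 50% × 13% = 6.5%. Against standard errors of 0.73 (2.54/√12) or 1.04 (3.59/√12), such an effect is detected almost surely without adjustment. This also stands.

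Finally, enrolment is complete, an interim analysis was planned, and section III.7 has the team reviewing data at least monthly for efficacy as well as safety. A covariate chosen now may be post hoc, and the fix has to allow for that.

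**Conclusion.** The point holds in a limited form. A standardised pre-dose resting EE is scheduled on every Cohort 3 dosing day, and the plan assigns it no role in a primary comparison. Using it as a covariate needs no new data. It widens the 95% CI by about 1-3% if the correlation is zero, is roughly neutral near 0.2, and narrows the CI by about 11-13% at 0.5 and 27-28% at 0.7. These figures assume the joint three-dose model and a correlation the documents do not supply.

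Three stronger readings are not supported. The BAT endpoint and the N of 28 are untouched: on dosing days the tracer is injected only at +240 minutes, so BAT activity has no same-day pre-dose value. The BMR comparison is not shown to be underpowered: with SD 2.54% and 28 completers, power for 2.34% is already about 0.997, and only the interval would tighten. Nor should the adjustment be said to remove carryover. The documents give no evidence for that, and with study days as little as 48 hours apart the pre-dose reading could itself contain any residual effect of the previous dose.

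**What to change.** State the Cohort 3 BMR analysis as follows:

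- Outcome: post-dose resting EE in the 10:30-11:00 and 12:40-13:10 windows.
- Model: within-subject, with dose, period and fixed subject effects, and that day's pre-dose EE as covariate. If subject effects are random, split the covariate into the subject mean and the within-subject deviation.
- Baseline: the 08:30-09:00 window, using only minutes before the actual dose, because dosing may occur as early as 08:45.
- No simple change score.
- Sensitivity analysis: the unadjusted paired difference, reported alongside.

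Fix this before EE is seen by treatment. If that point has passed, label the adjusted analysis post hoc and keep the unadjusted difference visible.

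The cost is analysis wording, one degree of freedom, and a CI up to about 3% wider if the correlation is near zero. No visit, measurement or sample size changes.

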Using a different set of assumptions leads to a higher predicted effect, or the upper bound expectation. We found that after the 200 mg dose, the estimated mean peak plasma concentration (C_{max}) of mirabegron was 274 ± 64 nM based on 65% protein binding, which is 6.9x the K_i of mirabegron for the $\beta 3$ -AR (40 nM) (FDA 2012). If the 50 mg dose achieves 18% of 200 mg, then the C_{max} would be 49 nM, which is 1.2x the K_i and 2.2x the in vitro EC_{50} of 22.4 nM (Takasu et al., 2007). Therefore, 50 mg mirabegron could produce $\geq 50\%$ of the effect seen with 200 mg, or ≥ 1.00 log BAT activity. Therefore, for 50 mg mirabegron, the effect on log BAT activity ranges from 0.36 to ≥ 1.00 .

For sample standard deviation, the log BAT activity after treatment with 0 mg mirabegron was 0.05 ± 0.62 and after treatment with 200 mg mirabegron was 2.00 ± 0.79 . Assuming a linear relationship between dose and standard deviation of the outcome variable, for the 50 mg dose of mirabegron, the standard deviation for log BAT activity is predicted to be 0.66.

In summary, we are planning a study of a continuous response variable from study subjects where each acts as his own paired control. Assuming the true difference between 0 mg mirabegron and 50 mg mirabegron is 0.36 with a standard deviation of 0.66, we will need to study 28 subjects to be able to reject the null hypothesis that this response difference is 0 with $\alpha=0.05$ and power of 80%. However, if the response is 1.00, then we will need to study only 6 subjects. Given this wide range (6-28 subjects), we will plan to complete 28 subjects with an interim analysis after 12 subjects. If the results of the interim analysis suggest that the response is closer to the upper bound estimate, then we will be able to reject our null hypothesis at that point. A sample size of 12 was chosen because if 12/12 subjects show higher BAT activity with the 50 mg, then non-parametric paired comparison yields a P value of 0.001.

For these types of studies, we have experienced a screen-failure rate of 50% and a rate of detectable BAT of 66%. We therefore plan to enroll up to 84 subjects, perform Study Day A in 42, and expect 28 to complete all four study days. If we are able to complete the study after the interim analysis, then we would end up enrolling 36 subjects, initiate the screening protocol with 18, and have 12 complete all four study days.

III.2-1 Protocol design, Cohort 1 – This Cohort has completed enrollment

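### Cohort 3: the objectives give primary status to four mirabegron-placebo tests, the power section to one, and no multiplicity rule is worked out for the cohort

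*Combined protocol and SAP*

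**What the plan says.** Section II.1 (Primary Objectives, Cohort 3) has two objectives. One compares the three dose levels on BAT metabolic activity. The other is "To compare the effects of mirabegron at 0mg, 50mg, and 200mg on BMR". The first hypothesis is that "Mirabegron at 50mg and 200mg PO will each increase BMR and BAT activity more than placebo". A second hypothesis under the same heading concerns safety: "The increases in heart rate and systolic BP after a one-time dose of 50mg will be lower than that observed using 200mg".

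The power calculation in III.1 is narrower: "In Cohort 3, the primary endpoint is the difference in detectable BAT activity", and the contrast is "between the 0 mg and 50 mg doses of mirabegron". The sample size follows from it: "Assuming the true difference between 0 mg mirabegron and 50 mg mirabegron is 0.36 with a standard deviation of 0.66", with alpha 0.05 and power 80%, 28 subjects are needed. If the difference is 1.00, "then we will need to study only 6 subjects". An interim analysis is planned after 12 subjects, at which the null may be rejected. No boundary or alpha split is given.

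The only multiplicity text, also in III.1, offers Bonferroni as the most conservative reading. It works out 0.05/5 for Cohort 2 and 0.05/4 for Cohort 1, and nothing for Cohort 3.

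**The concern.** The two sections disagree on what counts as a primary result. Under III.1 there is one primary test. Under II.1 there are four: BAT and BMR, each at 50 and 200 mg against 0 mg. A team following II.1 could report a lone success on BMR, or at 200 mg, as a primary finding at 0.05 when the cohort was neither sized nor adjusted for it. The multiplicity sentence refers to comparisons within each cohort and might be stretched to Cohort 3, but the sizing there uses the full 0.05. What is at stake is which positive results from Cohort 3 may be called confirmatory.

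**Working it through.** **1. The plan's own sample size.** Inputs from III.1: difference 0.36 or 1.00 in log BAT activity, SD 0.66, paired design, alpha 0.05. Sidedness is not stated.

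- Power of a two-sided paired t-test = P(|T| > t(0.975, n−1)), with T noncentral t and noncentrality (difference/SD)·√n.
- For 0.36 at n = 28: (0.36/0.66)·√28 = 2.886, critical value 2.052, power 0.795. Power first passes 0.80 at n = 29; the normal approximation gives 27. The stated 28 is reproduced to within one subject.
- For 1.00, n = 6, as stated.
- A one-sided test would give 23 and 5, so two-sided fits the plan better.

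**2. Familywise error of four tests at 0.05, one final analysis.**

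| Assumption | Familywise error |
|---|---|
| All four nulls true, tests independent: 1 − 0.95⁴ | 0.185 |
| All four nulls true, shared 0 mg day (correlation 0.5 within an outcome), BAT and BMR independent, simulated | about 0.175 |
| All four nulls true, every pair correlated 0.5, simulated | 0.157 |
| 200 mg effects real, two 50 mg nulls true, independent: 1 − 0.95² | 0.0975 |

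**3. The interim look.** The information fraction is 12/28 = 0.429, so the two test statistics correlate √0.429 = 0.655. Testing one true null at two-sided 0.05 at both looks gives P(|Z₁| > 1.96 or |Z₂| > 1.96) = 0.085 by normal theory, and about 0.087 with simulated t-tests. If the interim were instead tested at 0.001, the P value that III.1 attaches to a 12-of-12 result, the total would be 0.0503. The plan does not say which threshold applies. Four tests at 0.05 at both looks, with a shared 0 mg day, give about 0.29.

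**4. Cost of possible corrections to BAT at 50 mg (difference 0.36, SD 0.66).**

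- Bonferroni over four, alpha 0.05/4 = 0.0125: power 0.588 at n = 28; 41 subjects needed for 80%.
- Fixed sequence BAT 200, BAT 50, BMR 200, BMR 50, each at 0.05: only BAT 200 stands ahead of BAT 50. The pilot difference is 2.00 − 0.05 = 1.95. The SD of the paired difference is not given. Pilot SDs of 0.62 and 0.79 give √(0.62² + 0.79²) = 1.00 if the days are uncorrelated, and at most 0.62 + 0.79 = 1.41. At n = 28 the gate has power above 0.9999 for any SD from 0.66 to 1.41 (at n = 12, 0.991 at SD 1.41). BAT 50 therefore keeps 0.795.
- Putting BMR 200 ahead of BAT 50 is less safe. The background gives a 13% rise in RMR at 200 mg with no SD. For assumed SDs of 10 and 12 points, that gate has power 0.983 and 0.926 at n = 12. At n = 28 and SD 20 it is 0.912, which lowers BAT 50 to 0.912 × 0.795 = 0.72.

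**5. Sequence plus interim boundary.** An O'Brien-Fleming boundary at 12/28 uses nominal 0.0026 at the interim and 0.0489 at the end. It restores 0.05, and power for BAT 50 at the final nominal level is 0.792.

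**6. BMR at 50 mg, tested last.** Assume an effect of 18% of 13% = 2.34%, and independence of the two outcomes. Unconditional power at n = 28 is 0.897 at SD 3.7 and 0.666 at SD 5. After BAT 50 these become 0.795 × 0.897 = 0.71 and 0.795 × 0.666 = 0.53.

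**The case against.** The strongest reply is that III.1 already settles the matter. It designates one endpoint and one contrast and sizes nothing else, so the named test has its 0.05 and the rest is loose labelling. Likewise, if the hypothesis in II.1 counts as supported only when all four effects are shown, no adjustment is needed. Both readings are possible, but the plan states neither. Primary status in II.1 remains as written, so the sections still need reconciling. What stands is that the smallest sufficient repair is to relabel three tests as secondary; a sequence is optional.

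The size of the error is also open to challenge. The 0.17 to 0.18 needs all four nulls to be true, yet the pilot suggests large 200 mg effects. If those are real, only the two 50 mg tests can give false positives, and the figure is about 0.10. That objection stands.

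A reader might infer that a positive BMR result at 50 mg is what would carry that dose into later work. The documents do not say so. The background section makes continued use depend on 50 mg being effective enough, without tying that to BMR or to any one endpoint.

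**Conclusion.** The point holds as an inconsistency with a consequence for claims: four primary tests in II.1, one in III.1, and no worked-out error control for Cohort 3. Its size at a single final analysis is about 0.17 to 0.18 with all nulls true and outcomes independent (0.157 if every pair correlates 0.5), or about 0.10 if the 200 mg effects are real.

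A reader might infer that a fixed sequence alone would bring all four tests to 0.05. It would for one final analysis, but the plan allows rejection at 12 subjects without a boundary, and testing at 0.05 there takes a single test to about 0.085. A reader might also infer that starting with both 200 mg tests is free of cost. That holds for BAT at 200 mg on the pilot figures. For BMR at 200 mg it rests on an SD the documents do not give, and it would put the declared primary endpoint behind a test the cohort was not powered for.

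The 0.795 rests on the plan's own inputs. The 0.36 is 18% of the 200 mg level of 2.00; taken as a difference from the 0 mg level of 0.05 it would be 0.31, with power 0.67. That is a separate matter and does not change the comparison between corrections.

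**What to change.** Amend II.1 to agree with III.1: BAT activity at 50 mg versus 0 mg is the single primary test in Cohort 3. Then choose one of two treatments for BAT at 200 mg and BMR at both doses.

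- Label them secondary, reported with confidence intervals and no primary claim.
- Or test in a fixed sequence at two-sided 0.05 that never puts a BMR test ahead of BAT at 50 mg. An example is BAT 200, BAT 50, BMR 200, BMR 50, with formal claims ending at the first non-significant step.

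In either case state an alpha-spending boundary for the look at 12 subjects, such as the O'Brien-Fleming split above, and apply it to every test in the sequence. The P value of 0.001 that III.1 gives for a 12-of-12 result lies below its interim level of 0.0026. Keep heart rate and systolic blood pressure outside the sequence, as estimates with confidence intervals.

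The order must be fixed before any unblinded or interim result is known. This matters because Cohort 3 has completed enrollment, and the documents call it single-blind in III.2-3 but open label in the Data and Safety Monitoring Plan. If results are already known, keep BAT at 50 mg versus 0 mg as the only primary test and report the other three as secondary.

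The cost is analysis wording, with no added subjects or visits. The downside of the sequence is that BMR at 50 mg, if last, becomes descriptive whenever an earlier step fails, and its power cannot exceed that of BAT at 50 mg.
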